#### Exploratory analyses

##### *Time to sleep onset (TSO)*

To determine whether times to sleep onset differ between treatment groups, we will analyze data using a Student's t test, or Mann-Whitney-U test, as appropriate.

#### *Delirium*

To determine whether incidence of postoperative delirium and delirium free days differ between treatment groups, we will analyze data analogously to the primary and secondary analyses.

#### *Variability in response to suvorexant treatment*

To determine whether there is an association between each of the previously described potential confounders and TST during the night of the sleep trial, we will use logistic regression models. Subsequently, we will evaluate a potential interaction between any statistically significant predictor of TST and suvorexant treatment on total sleep time.

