#### *Variability in response to suvorexant treatment*

We will determine whether the effect of suvorexant are modified by the following patient, procedure, and anesthesia-related factors: subjective TST during the nights prior to surgery measured by RCSQ, , cardiovascular function impairment (norepinephrine equivalent dose), duration of mechanical ventilation, total propofol dose since skin incision, and markers of pain intensity such as total opioid dose since skin incision for up to 48 hours postoperatively and numeric rating scale (NRS) pain scores (scale from 0 [no pain] to 10 [worst pain]) [23] obtained by nursing staff blinded to treatment allocation on each evening before study drug administration for 7 days. To account for surgical complexity as a marker of postoperative stress response, we will further include duration of bypass time, total blood loss, and the Procedural Severity Score for mortality (PSS mortality).

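### Effect-modification analysis: logistic regression is named for a sleep time in minutes, interactions are tested only for factors that already predict TST, and several factors are not fixed at the first dose

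*Combined protocol and SAP*

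**What the plan says.** The aim is stated in section B3.A, Variability in response to suvorexant treatment: "We will determine whether the effect of suvorexant are modified by the following patient, procedure, and anesthesia-related factors". The exploratory objectives (B1) and the Study endpoints list (B3.A) pose the same question.

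The method is in the section of the same name in B3.B and has two steps:

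- Step 1 concerns the association between the "potential confounders and TST during the night of the sleep trial, we will use logistic regression models".
- Step 2 follows from it: "we will evaluate a potential interaction between any statistically significant predictor of TST and suvorexant treatment on total sleep time". No model is named for this step.

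Nine factors are legible in the B3.A list:

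- "subjective TST during the nights prior to surgery measured by RCSQ"
- three factors given as "cardiovascular function impairment (norepinephrine equivalent dose), duration of mechanical ventilation, total propofol dose since skin incision"
- "total opioid dose since skin incision for up to 48 hours postoperatively"
- pain scores taken "on each evening before study drug administration for 7 days"
- "duration of bypass time, total blood loss, and the Procedural Severity Score for mortality (PSS mortality" (three factors)

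Elsewhere TST is a time. It is measured in the same way as WASO, which is defined in minutes (Assessment of study endpoints), and it is compared between arms by t test or Mann-Whitney test (Primary and secondary analyses). It is recorded on one night only.

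**The concern.** There are four separate problems.

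1. **Model.** Logistic regression needs a binary or ordered outcome. The plan turns TST into neither, so someone must choose a cut-point or another model at analysis. Analysts are blinded to arm, but the pooled association between a factor and TST, which decides what passes step 1, can be seen without the allocation.
2. **Screen.** Whether a factor predicts TST and whether it changes the drug effect are different questions. A factor whose slopes differ between arms can show little pooled association and never reach step 2.
3. **Timing.** A modifier should be fixed before treatment. Values that accrue after the first dose may be affected by the drug, and some would post-date the TST night altogether.
4. **RCSQ.** Its five items are 0 to 100 visual analogue ratings. None is a sleep duration, so the factor has no definition.

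At stake is whether the stated exploratory question is answered and whether the result could be reproduced from the plan.

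**Working it through.** **The plan's own figures.** None is given for this analysis. The sample-size figures do reproduce: WASO, 30 min, SD 45, 50 per group, t-test power 91.0% (plan: above 90%); delirium-free days, 3 days, SD 5, power 84.4% (plan: 84.4%).

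**Assumptions.** The documents give no SD for TST. I take a residual SD of 60 min and show 45 to 90, where 45 is the plan's WASO SD. There are 50 patients per arm, a treatment effect of 30 min, a normally distributed factor scaled to SD 1, and two-sided tests at 0.05. The model is TST on treatment, factor, treatment × factor and a binary stratum.

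**Precision of the interaction.** For a normal factor with 50 per arm, the mean of 1/Sxx in an arm is 1/47. Hence SE ≈ SD × √(2/47).

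- SD 60: 60 × 0.2063 = 12.4; × 1.985 gives a 95% half-width of 24.6 min per SD.
- SD 45: 18.4. SD 90: 36.9.

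Simulation gives 24.5–24.6, 18.4 and 36.9.

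**Direct test.** Power ≈ Φ(interaction/SE − 1.985). At SD 60, an interaction of 40 gives Φ(3.23 − 1.985) = 89%; 30 gives 67%; 20 gives 36%.

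**Cost of the screen.** Step 1, pooled over arms, sees roughly the average of the two arm slopes. Simulated detection (4,000 runs per cell), direct / through a linear screen, interaction 40 min per SD:

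| Slopes, placebo / suvorexant | Average slope | SD 45 | SD 60 | SD 90 |
|---|---|---|---|---|
| −20 / +20 | 0 | 99 / 7% | 89 / 5% | 58 / 3% |
| −10 / +30 | 10 | 99 / 47% | 88 / 30% | 57 / 10% |
| 0 / +40 | 20 | 99 / 94% | 89 / 74% | 56 / 31% |
| +20 / +60 | 40 | 99 / 99% | 89 / 89% | 57 / 56% |

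At SD 60, in the same row order, an interaction of 30 gives 66/4, 66/14, 67/43 and 67/67%; an interaction of 20 gives 36/2, 37/5, 36/13 and 37/33%.

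A separate check with a balanced binary factor (SD 45, interaction 60 min) agrees. Direct detection is 91%. If the factor acts only on suvorexant, it is 73% through a linear screen and 52% through a median split. With opposite slopes it is about 1–2% through either.

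**Cost of the unstated model.** Slopes 0/+40, SD 60, detection through the screen: linear 75%, ordinal 71%, median split 50%, lower-quartile split 35%. The last three are 92, 73 and 53% at SD 45, and 28, 18 and 13% at SD 90.

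**False positives.** With common slopes of 0, 10, 20 and 30 min per SD at SD 60, false interactions through the linear screen occur in 0.2, 1.6, 4.5 and 5.0% per factor. Over nine independent factors, 1 − (1 − p)^9 gives 2, 14, 34 and 37%. Direct tests give 1 − 0.95^9 = 37%.

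**Windows.** Opioid dose and pain scores have written windows that can pass the first dose. Norepinephrine equivalents, propofol and blood loss have no stated end. That makes 2 + 3 = 5. Ventilation duration is a possible sixth after reintubation. For opioids, assume surgery ends between noon and 6 pm, with dosing at 9 pm and the TST night ending at 6 am:

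- First dose that evening: the night ends 18 to 12 h after surgery, so the 48 h window ends 48 − 18 = 30 to 48 − 12 = 36 h after it.
- First dose the next evening: 48 − 42 = 6 to 48 − 36 = 12 h after the night.
- First dose on the third evening: that dose comes 57 to 51 h after surgery, so the window closes 9 to 3 h before it.

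**The case against.** The strongest reply is that this is the last-listed exploratory outcome, carries no power claim, and leaves the primary and secondary comparisons alone. That is right and limits the weight of the point. It does not supply a missing model for a stated objective.

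Next, the candidates are described as causes of insomnia, so they should predict TST, and for such factors the screen costs little. At SD 60, slopes of −50/−10 give 88% direct and 87% screened; −30/−10 give 36% and 31%. This stands: the fall to 5% needs exactly opposite slopes, for which the documents give no basis. But a factor acting mainly in one arm still loses, and the plan cannot know in advance which pattern holds.

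On timing, only opioids and pain are written to run past the first dose. The first-evening pain score is usable, and propofol, norepinephrine and blood loss have a natural pre-dose reading. That reading is reasonable but unstated. The 36 h opioid figure is an edge case, because a same-evening dose requires extubation before 7 pm.

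The 37% familywise figure assumes independence; under equal correlations of 0.3, 0.5 and 0.7 it is 33, 27 and 20%. The screen does not inflate false positives. The power figures measure detection, whereas the remedy reports estimates, so they show what the screen hides rather than what the remedy will prove. Adjusting for the stratum is a choice, since the main comparison is unadjusted.

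**Conclusion.** The concern holds. The named model does not fit TST as defined, the interaction model is missing, the screen answers a different question from the stated aim, at least five factors are not closed at the first dose, and one factor cannot be derived from its instrument. These follow from the text and need no assumed SD.

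The size of the power loss does depend on assumptions: the TST SD, a normal factor, 100 patients and the pattern of arm slopes. It runs from nil (prognostic in both arms) to nearly total (opposite slopes). With the factor active only on suvorexant and an interaction of 40 min per SD, it is 89% to 74% at SD 60. An interaction of 40 min per SD is large, exceeding the plan's 30 min WASO difference. This should be corrected before unblinding, but it bears on an exploratory outcome only.

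**What to change.** Replace the two-step text in B3.B with one model. For every factor listed in B3.A, fit a linear regression of TST in minutes on treatment, factor, treatment × factor and the randomisation stratum, with no significance screen. Report each interaction estimate with its 95% CI as exploratory, without significance claims.

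In B3.A:

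- Use the first-evening pain score, and take opioid, propofol and norepinephrine dose and blood loss up to the first study dose. Apply the same pre-dose rule to any other time-varying factor.
- Replace subjective TST with a preoperative RCSQ score defined in the plan.
- If circadian disruption and comorbidities, named in the objectives and endpoints, are to be analysed, name their variables. The factor list has a blank, so no omission is claimed.

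The cost is wording; no measurement beyond those planned is needed. The limits should be stated. Precision is low: the half-width is about 24–25 min per SD at SD 60 (18 at SD 45, 37 at SD 90). A strongly skewed factor gives a median of 26 (10th to 90th percentile 23 to 34, without the stratum term). Overlap between stratum and factor made no material difference in simulation (24.4–24.6). Anyone who reads nine independent intervals as tests at 0.05 runs about a 37% chance of a false positive. The present screen protects little against that when factors are prognostic.

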#### *Safety*

Incidence of serious and non-serious adverse events will be compared between the two groups using a Chi-Square test. Specific comparisons will further include somnolence, fatigue, headache, dry mouth, cough, and upper-respiratory infections as well as abnormal thoughts and behaviors, hallucination, memory loss, anxiety, sleep paralysis, and lower-extremity weakness.

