#### Randomization and blinding

After postoperative extubation, eligible patients will be randomly allocated in a 1:1 ratio to receive either suvorexant 20 mg or placebo. If extubation is planned outside of research pharmacy hours, randomization and drug preparation will take place in coordination with research and hospital pharmacy in accordance with their policy. Randomization will be performed by computer-generated variable block size random allocation stratified by duration of perioperative anesthesia and sedation, using a cut-off value of 420 minutes of perioperative sedation (i.e. duration of anesthesia and postoperative sedation of equal to or over 420 minutes). The allocation sequence will be provided to the research pharmacy. To achieve blinding, the study drug and placebo will be delivered in the form of non-identifiable pills, containing either the active ingredient suvorexant, or lactose. Individual patients' drug bottles will be labeled with randomization numbers. Randomization number-specific codebreakers, prepared by the research pharmacy, will contain information about a patient's treatment allocation in a sealed envelope and will be kept in the patient's study record. If unblinding procedures are necessary for clinical reasons, the clinical team will be able to contact a member of the research team with access to the codebreaker at any time by pager or phone. The codebreaker envelope is only to be opened with PI approval as instructed on the envelope. The PI will immediately inform the research pharmacy and study team of any unblinding procedures. Delivery of research medication to the patient care area will take place per pharmacy guidelines. Disposal of any unused study medication will be done per pharmacy guidelines.

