#### Study interventions

Suvorexant 20 mg or placebo will be administered p.o. once a day at 9:00 pm for a maximum of 7 days starting the night after extubation in the ICU. A one-hour window (9:00 pm-10:00 pm) to administer the drug will ensure protocol adherence in case of delays in drug administration. Prior to every study drug administration, the Richmond Agitation-Sedation Scale will be assessed. In case of RASS < -1, the study drug will not be administered on that same day. The study drug will be discontinued:

1. After 7 consecutive doses following extubation; or

2. At hospital discharge (if less than 7 days after extubation); or
3. At ICU discharge, if patient showed signs of airway obstruction during sleep; or
4. At ICU discharge or after a maximum of 3 consecutive doses, whichever occurs sooner, if strong inhibitors of CYP3A (e.g. digoxin, diltiazem, verapamil) are co-administered; or
5. In the event of early termination: subject withdraw of consent, investigator withdrawal for toxicity or other reasons.

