## **B. Statistical Considerations**

### **Sample Size Justification**

We will consider a 30 minute difference in WASO as clinically meaningful, with a standard deviation (SD) of 45 minutes [24]. Accordingly, we expect that a sample size of 50 subjects per group will provide us with >90% power to detect this difference between treatment groups, using a two-sample t-test with 2-sided  $\alpha=0.05$ . As for the exploratory outcome, we may see a difference of 3 delirium-free days (this assumption is based on findings observed with early mobilization by us in a similar cohort [25]) between groups with a SD of 5 days. The given sample size of a total of 100 patients will yield a power of 84.4% to detect a difference in the exploratory

outcome. To account for drop-out, we plan to enroll up to 120 patients to achieve our desired sample size of 100 completed participants.

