### **Data Analysis**

The statistical analyses will be initiated by blinded study team members supervised by a BIDMC statistician. All study personnel will be blinded to the treatment group of the subject, except the investigational pharmacist. For the purpose of the final analysis, unblinding will be performed by the statistician and the research team. The research database will not be unblinded until the medical/scientific review has been completed, protocol violations have been identified (if appropriate), and data collection has been declared as complete.

All analyses will be conducted by research staff supervised by a BIDMC statistician and performed in Stata (StataCorp LP, version 13.0 or higher) and Rstudio (Rstudio.INC, Boston, MA, Version 1.1.4638). All personnel involved in data analyses will be blinded to intervention group assignment. A two-sided P value of <0.05 will be considered statistically significant.

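### Adverse events are compared only by chi-square tests, with no effect estimate or confidence interval; for uncommon events at about 50 per arm, a non-significant result says little about harm

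*Combined protocol and SAP*

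**What the plan says.** The Safety paragraph under Exploratory analyses (section B3.B) is the complete safety analysis. It states: "Incidence of serious and non-serious adverse events will be compared between the two groups using a Chi-Square test". It then names particular events, in two groups of six. One group is general symptoms, from somnolence to respiratory infection. The other is mainly neuropsychiatric: "as well as abnormal thoughts and behaviors, hallucination, memory loss, anxiety, sleep paralysis, and lower-extremity weakness". That makes 12 named events, besides the serious and non-serious categories.

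The paragraph sets no threshold of its own. The general rule under Data Analysis therefore applies: "A two-sided P value of <0.05 will be considered statistically significant".

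The Sample Size Justification covers WASO and delirium-free days and says nothing about safety. For WASO, "we expect that a sample size of 50 subjects per group will provide us with >90% power". On enrolment, "we plan to enroll up to 120 patients to achieve our desired sample size of 100 completed participants". Allocation is 1:1, so the safety comparison will have 50 to 60 patients per arm. The documents do not define a safety population.

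No section gives an expected adverse event rate. None plans a risk difference, risk ratio, confidence interval or small-count method for adverse events.

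**The concern.** The trial gives a sleep-promoting drug to patients aged 60 or older, starting soon after extubation following cardiac surgery. Its safety table will be read for what it says about tolerability in that setting. The protocol already regards the drug's side effects as minor (section B5, citing the package insert), so a column of non-significant p-values could easily be taken as confirmation.

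A chi-square p-value answers only whether a difference was detected. In a trial sized for a continuous sleep outcome, the expected answer for an uncommon event is no, whether or not the drug causes it. What a reader needs is the range of excess risk that the data leave open, and the plan does not commit to reporting it.

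**Working it through.** **Inputs from the documents.** Two-sided alpha 0.05 (Data Analysis); 50 completers per arm, up to 60 enrolled per arm (Sample Size Justification); 1:1 allocation; chi-square test (Safety).

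**Input assumed.** The control-arm event rate, which the documents do not give. The range examined is 1% to 30%.

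**Step 1: the plan's own power figures.** For a two-sample t-test with 50 per arm, the noncentrality is (difference/SD) × √(50/2).
- WASO: (30/45) × 5 = 3.33, giving power of 91.0%. The plan says above 90%.
- Delirium-free days: (3/5) × 5 = 3.00, giving power of 84.4%. The plan says 84.4%.

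Both reproduce. Neither bears on adverse events.

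**Step 2: chance of missing a doubled event rate.** For every pair of counts (i, j) in two arms of n, take the binomial probability of that pair and compute the uncorrected Pearson statistic, 2n × [i(n − j) − j(n − i)]² / [n × n × (i + j) × (2n − i − j)]. The test rejects when this exceeds 3.84. The miss rate is 1 minus the summed probability of the rejecting pairs.

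| Control rate → doubled rate | Miss rate, 50 per arm | Miss rate, 60 per arm |
|---|---|---|
| 1% → 2% | 98.9% | 98.1% |
| 2% → 4% | 94.6% | 92.8% |
| 5% → 10% | 85.5% | 82.6% |
| 10% → 20% | 69.7% | 67.4% |
| 15% → 30% | 55.7% | 48.6% |
| 20% → 40% | 40.5% | 31.6% |
| 30% → 60% | 12.4% | 7.6% |

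The plan does not say whether a continuity correction would be used. With Yates' correction at 50 per arm, the miss rates at 2%, 5% and 10% rise to 99.4%, 93.7% and 80.5%.

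**Step 3: sample size that would be needed.** For 80% power to detect a doubling, n per arm = [1.96√(2p̄(1 − p̄)) + 0.842√(p₁(1 − p₁) + p₂(1 − p₂))]² / (p₂ − p₁)², where p̄ is the mean of the two rates. For 10% versus 20%: (1.96 × 0.505 + 0.842 × 0.5)² / 0.01 ≈ 199. The same formula gives 435 at a 5% control rate and 1,141 at 2%.

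**Step 4: what an interval would add.** Suppose 10/50 versus 5/50 patients have an event. The statistic is 100 × (10 × 45 − 5 × 40)² / (50 × 50 × 15 × 85) = 1.96, below 3.84, so the result is not significant. The Wilson 95% limits are 11.2% to 33.0% and 4.3% to 21.4%. The Newcombe interval for the risk difference is then:
- lower: 0.10 − √[(0.200 − 0.112)² + (0.214 − 0.100)²] = −4.3 points
- upper: 0.10 + √[(0.330 − 0.200)² + (0.100 − 0.043)²] = +24.2 points

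Even a perfectly balanced 5/50 versus 5/50 leaves −12.7 to +12.7 points. The p-value shows neither range.

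**Step 5: small counts.** At 2% versus 4%, the expected number of events under the null is 50 × (0.02 + 0.04)/2 = 1.5 per arm, too few for the chi-square approximation to be trusted.

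**The case against.** The strongest reply is that the plan draws no wrong conclusion. It says only that incidence will be compared, it places safety among the exploratory analyses, and safety is not a listed objective or endpoint. A reader might infer that a non-significant test is to be taken as evidence of safety, but no sentence in the documents says so. This part of the reply stands: the gap is a missing estimate and interval.

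Second, the miss rates depend on rates that the documents do not supply. This also stands. A reader might conclude that the tests would usually overlook any two-fold or three-fold excess. The arithmetic does not support that. A doubling from 30% is missed only 12.4% of the time at 50 per arm, and a tripling from 10% to 30% only about 27%. Any non-serious event, or a symptom such as fatigue, could well be common after cardiac surgery. The weakness lies with uncommon events.

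Third, a reader might think that the named list leaves out harms on which the protocol acts, since one stopping rule reads "At ICU discharge, if patient showed signs of airway obstruction during sleep; or" and doses are withheld for RASS below −1. The documents do not support treating this as an omission. The named events are additional to all serious and non-serious events, so an airway event that qualifies as an adverse event is already counted. The RASS check is a pre-dose assessment and is not defined as an adverse event.

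Fourth, low power for adverse events is inherent in a trial of this size, and anyone given counts by arm could work out an interval. Both are true. But low power is the reason to plan for estimation, and the Safety paragraph does not commit to reporting those counts and percentages. Frequencies and percentages are specified only in the context of baseline characteristics.

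**Conclusion.** The point holds as a gap in analysis and reporting. Chi-square tests at 0.05 are the only safety analysis specified, and no effect estimate or interval is planned for any adverse event. For assumed control rates of 2% to 10%, the uncorrected test misses a true doubling about 95% to 70% of the time at 50 per arm, or 93% to 67% at 60 per arm. The figure is higher for rarer events and lower for commoner ones (41% at a 20% control rate with 50 per arm). The undefined safety population moves the 2% to 10% results by only about 2 to 3 points. A non-significant result for an uncommon event would therefore say little about harm. The primary analysis is unaffected. This is a worthwhile and inexpensive improvement; it does not show that the plan reaches a wrong safety conclusion.

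**What to change.** Amend the Safety paragraph in section B3.B as follows.

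- For serious events, non-serious events and each of the 12 named events, report the number and percentage of patients with at least one event, by arm.
- For each, give the risk difference with a 95% Newcombe or Miettinen-Nurminen interval.
- Keep p-values as descriptive only, and use an exact method where counts are small.
- State that p>0.05 will not be reported as absence of harm.

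This costs a few sentences and a few table columns, with no additional patients, visits or procedures. The intervals will be wide, so the safety statement will be less reassuring than a list of non-significant p-values.
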